4.2 Exclusion criteria

- Acute worsening of previous diagnosed chronic disease where there is no suspicion of comorbidities (for example when a patient with clear COPD diagnosis has an exacerbation where typically the HCP will not perform additional tests).
- 2. Inability to understand and sign the written consent form.

4.3 Sample size determination

The sample size was determined to reliably demonstrate that there is a difference in the number of days between presentation with breathlessness in the clinic and diagnosis of a disease or disorder causing this breathlessness between usual care and the BiaB intervention.

For stepped-wedge clustered designs, the sample size is a combination of the number of clusters, the number of sequences, the number of time periods and the number of individuals per cluster period.⁷ Research shows that the best method of estimating the required sample size for a

stepped-wedge design is to simulate the power based on the method of analysis proposed including time in the chosen model.^{8,9} Therefore, for this study a sensitivity analysis has been performed using a desired power of 80% for the test of the intervention, with a type I (two-tailed) error rate of 0.05. The analysis was performed using the US National Institute for Health Stepped-wedge Group-Randomized Trials (SWGRT) Calculator software.¹⁰

The following assumptions were considered:

- The expected cluster autocorrelation (between two consecutive periods at the cluster level) was estimated 0.8, as healthcare professionals (HCPs) will use standard protocols or guidelines which are not expected to change between consecutive (6 week) periods within the study period.
- The intra class correlation was set to 0.03 based on previous data.¹¹
- The expected individual autocorrelation (between two consecutive periods at the level of the patient) was estimated 0.8, as HCPs will use standard protocols or guidelines which are not expected to change between consecutive (6 week) periods within the study period.
- The decay-structure for over-time correlations is Block-exchangeable.
- The churn rate was set to 0.0, as the study consists of one visit for data collection and data essential for the primary objective can be retrieved from HCPs.
- The number of patients per sequence (3 practices) is 60.
- Variation in cluster size is not taken into account as 60 patients will be included per cluster for analyses.
- The expected distribution of the primary outcome, dichotomous was set to 0.3.
- There are 6 time periods (including usual care and BiaB intervention period).
- The hypothesized intervention effect as a difference of time to diagnosis from presentation with breathlessness between usual care and BiaB intervention is 0.2 (20% reduction of time to diagnosis (in days) based on data from the BiaB pilot study, assumed differences between countries the assumption that the average time to diagnosis in usual care will be 70 days and the assumption that a reduction of 14 days is assumed clinically relevant). The 70 day period is chosen after discussions with the scientific advisory board,

including general practitioners, pulmonologists and cardiologist from the Netherlands, Spain and the United Kingdom, because after an extensive literature search, no timed pathway could be found. This 70 days is based on knowledge of access times to several diagnostic tests and clinical experience.

Calculations showed that with 60 patients per cluster (20 patients per site, 5 sequences, 3 countries) and 3 sites per sequence per country we have sufficient power to detect an absolute difference in effect of 0.055 and a standardized detectable difference of 0.114 (i.e. 5.5-11.4%, respectively).

When assuming the outcome as a continuous effect of 0.2 with a variance of 0.1, we would have sufficient power to detect an absolute difference in effect of 0.0362 and a standardized detectable difference of 0.1144 (i.e 3.6 and 11.4%).

In terms of feasibility, Okkes et al. show an average of 2 to 3 patients present with breathlessness per primary care facility in the Netherlands monthly,¹² and other research shows the prevalence of breathlessness is even higher in Spain.¹³ This means the determined study period is sufficient to find 20 patients to participate per site during the study.

5. BiaB procedures

A BiaB-app has been designed to create an efficient workflow and to guide the healthcare professional (HCP) through the diagnostic process, by instructing to perform several tests and subsequently providing automatic interpretation of the results. All test equipment (all CE marked) will be available in the BiaB-box (figure 3) and can be performed by an HCP following a consultation for breathlessness. The BiaB-procedures will take approximately 20 minutes in total (based on the pilot study) and require limited training as all separate tests and the BiaB-application (BiaB-app) have been designed with usability in mind. During a BiaB visit, the entire box with all its tests will be conducted, except for the D-dimer test and YEARS criteria, which will be administered only if pulmonary embolism is suspected.

Clinical history

General characteristics of the patient are collected in the BiaB-app, including gender, age, height, weight, duration of dyspnea symptoms, and whether pulmonary embolism (PE) is suspected.

These characteristics are necessary input for the BiaB-algorithm to provide an accurate result.

The following tests are included:

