2. OBJECTIVES

Primary objective:

• To demonstrate whether BiaB use shortens time to diagnosis as compared to usual care without BiaB use.

Secondary objectives:

- To demonstrate whether BiaB use increases the number of new diagnoses of COPD and/or heart disease as compared to usual care without BiaB use
- To demonstrate usability and efficiency of BiaB.

3. Study design

A prospective stepped-wedge study design will be used for this study (Figure 4). In every country, participating sites will be assigned randomly to one of the five sequences (3 sites per sequence) for timing of the intervention start. Each sequence starts with a usual care period (6 weeks or a multiple of 6) which will be followed by a transition period of 4 weeks prior to the BiaB intervention

period (6 weeks or a multiple of 6). During the transition period the healthcare professionals (HCPs) at the site will be instructed about the start date of the BiaB intervention and they will receive training for the use of BiaB. The study duration for sites is 40 weeks in total. The maximum study duration for patients is one visit followed by a maximum of 4 quarterly questionnaires (1 year).

There will be 15 sites per country, amounting to a total of 45 sites for The Netherlands, Spain and Portugal. Per site 20 patients will be included for analysis during the 40-week study period, amounting to 300 patients per country and 900 in total for 3 countries. Per site the number of patients seen in the usual care period and BiaB intervention period will differ, but at the end of the study this study design should yield a ratio of 1:1 (usual care or BiaB intervention).

[figure not shown]

Figure 42. BiaB stepped-wedge study design. All sites (15 per participating country) will be randomly assigned to one of the sequences with set periods of usual care, transition, and BiaB intervention. In total 20 patients will be included per site, amounting to 300 patients per country and 900 patients in total.

Data will be collected (i) during the visit, and (ii) using questionnaires sent to patients and HCPs. Electronic medical data will be extracted from the participating GP practices before, during and at the end of the study. Data collected during the usual care period and, if possible, retrospective data will be used as a control to examine endpoints.

4. Study population

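### The detectable differences in section 4.3 treat every patient as measured in all six periods; with one outcome per patient they are about 2.5 times too small

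*Protocol*

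**What the plan says.** Section 4.3 reports a calculation made with a stepped-wedge calculator, "using a desired power of 80% for the test of the intervention, with a type I (two-tailed) error rate of 0.05". The settings that matter here are:

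- "The intra class correlation was set to 0.03 based on previous data".
- "The expected cluster autocorrelation (between two consecutive periods at the cluster level) was estimated 0.8".
- "The expected individual autocorrelation (between two consecutive periods at the level of the patient) was estimated 0.8".
- "The churn rate was set to 0.0, as the study consists of one visit for data collection".
- "Variation in cluster size is not taken into account as 60 patients will be included per cluster for analyses".
- Block-exchangeable correlation over time, six periods and five sequences.

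The conclusion drawn is "sufficient power to detect an absolute difference in effect of 0.055 and a standardized detectable difference of 0.114". A second version, for a continuous outcome with variance 0.1, gives 0.0362 absolute and 0.1144 standardised.

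Section 3 describes recruitment: "Per site 20 patients will be included for analysis during the 40-week study period", which makes 900 patients in 45 sites. Sections 3 and 6.4 give each patient a single visit. Section 6.1.1 defines one time to diagnosis per patient, taken from the first diagnosis. Section 6.2 makes the site the unit of randomisation.

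**The concern.** A patient-level autocorrelation between periods has meaning only if the same patient supplies an outcome in more than one period. Zero churn means that nobody is replaced from one period to the next. Here each patient presents once, under either usual care or BiaB, and has one primary outcome. That is a cross-sectional stepped wedge with complete turnover between periods. The reason given for zero churn, that there is only one visit, is a reason for the opposite setting.

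A closed-cohort calculation takes credit for two things the trial does not have: six measurements per patient, and within-patient comparison of usual care with BiaB. Both shrink the standard error. Separately, the calculation takes a group of three practices (60 patients) as the cluster, although single practices are randomised.

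At stake is the stated justification of the sample size. A reader would believe that the trial has 80% power for about a tenth of a standard deviation, and a null result would be read as excluding effects that the trial could not have seen.

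**Working it through.** **Method.** The variance of the intervention effect comes from generalised least squares on cluster-period means, with fixed period effects and block-exchangeable correlation. Let *m* be the patients per cluster-period, *d* the variance of a cluster-period mean and *c* the covariance of two means from the same cluster. The outcome variance is set to 1.

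- Within-period ICC: 0.03. Between-period ICC: 0.03 × 0.8 = 0.024.
- Both designs: *d* = (1 + (*m* − 1) × 0.03)/*m*.
- Closed cohort: *c* = (0.8 + (*m* − 1) × 0.024)/*m*. One outcome per patient: *c* = 0.024.

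With *I* clusters, *J* = 6 periods, λ₁ = *d* − *c* and λ₂ = *d* + 5*c*:

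Var = *IJ*λ₁λ₂ / [(U² + *IJ*U − *J*W − *I*V)λ₂ − (U² − *I*V)λ₁]

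U is the number of treated cluster-periods, W the sum of squared period totals and V the sum of squared cluster totals. The detectable difference is (t₀.₉₇₅ + t₀.₈₀) × √Var.

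**Step 1: reproduce the stated figures.** Closed cohort, *I* = 15, *m* = 60 in every period, df = 15 − 7 = 8.

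- U = 45, W = 495, V = 165. The coefficients are 2025 + 4050 − 2970 − 2475 = 630 and 2025 − 2475 = −450.
- *d* = 0.04617, *c* = 0.03693, λ₁ = 0.009233, λ₂ = 0.23083.
- Var = 90 × 0.009233 × 0.23083 / (630 × 0.23083 + 450 × 0.009233) = 0.19182/149.58 = 0.001282; SE = 0.03581.
- Standardised: (2.306 + 0.889) × 0.03581 = **0.1144** (stated 0.1144).
- Continuous, variance 0.1: 0.1144 × √0.1 = **0.0362** (stated 0.0362).
- Dichotomous, mean of the binomial variances at 0.3 and 0.5: √((0.21 + 0.25)/2) = 0.4796; 0.1144 × 0.4796 = **0.0549** (stated 0.055).

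This uses 15 × 60 × 6 = 5,400 measurements. The trial has 45 × 20 = 900.

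**Step 2: count each patient once, practices as clusters.** *I* = 45, *m* = 20/6 = 3.33, df = 45 − 7 = 38.

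- U = 135, W = 4455, V = 495. The coefficients are 18225 + 36450 − 26730 − 22275 = 5670 and 18225 − 22275 = −4050.
- *d* = 0.321, *c* = 0.024, λ₁ = 0.297, λ₂ = 0.441.
- Var = 270 × 0.297 × 0.441 / (5670 × 0.441 + 4050 × 0.297) = 35.364/3703.3 = 0.009549; SE = 0.0977.
- Standardised: (2.024 + 0.851) × 0.0977 = **0.281**.

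**Step 3: the same, keeping the protocol's 15 clusters.** *m* = 10, df = 8, *d* = 0.127, λ₁ = 0.103, λ₂ = 0.247.

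- Var = 90 × 0.103 × 0.247 / (630 × 0.247 + 450 × 0.103) = 2.2897/201.96 = 0.01134; SE = 0.1065.
- Standardised: 3.195 × 0.1065 = **0.340**.

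| | Stated | 45 practices | 15 clusters |
|---|---|---|---|
| Standardised | 0.114 | 0.281 | 0.340 |
| Continuous (× √0.1) | 0.0362 | 0.089 | 0.108 |
| Dichotomous (× 0.4796) | 0.055 | 0.135 | 0.163 |
| Ratio to stated | 1 | 2.46 | 2.97 |
| Power at 0.114 SD | 80% | about 20% | about 13% |

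With normal instead of t quantiles the ratios are 2.39 and 2.61. For an assumed ICC from 0.01 to 0.10, the 45-practice figure runs from 0.27 to 0.30 SD.

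**Step 4: a bound that needs no stepped-wedge model.** An individually randomised 1:1 trial of 900 patients, with no clustering and no period adjustment, detects 2 × (1.96 + 0.842)/√900 = 0.187 SD. The stated 0.114 SD is below that.

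**The case against.** The strongest reply is that the trial is planned for an effect of 0.2, not for 0.055 or 0.114. On the protocol's own scale every corrected absolute figure (0.089 to 0.163) is below 0.2. Power for 0.2 is about 98% or more with 45 practices and about 93% or more with 15 clusters. This stands: the error does not by itself show that 900 patients are too few. The comfort is conditional, however. If 0.2 is a fraction of the 70-day mean, a variance of 0.1 implies an SD of √0.1 × 70 ≈ 22 days, and the protocol gives no SD in days. For assumed SDs of 35, 50, 70 and 100 days, power for the 14-day target with 45 practices is about 98%, 80%, 51% and 28%. The closed-cohort calculation would show at least 93% throughout, so it conceals this dependence.

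Second, the factor of 2.5 combines two corrections that pull in opposite directions. Removing the repeated measurements alone gives 2.97; moving to 45 practices brings it back to 2.46. Grouping practices in threes was conservative: a closed cohort of 45 practices with 20 patients each would have given 0.078. This is correct, and it means the grouping does not explain why the figures are too small.

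Third, the 8 degrees of freedom and the averaged binomial variance are inferred; the protocol states neither. A cross-sectional run with 45 clusters and 30 patients per site-period also lands at 0.1142 to 0.1146. That would need 30 × 6 = 180 patients per site against the stated 20, so it does not rescue the figure. The bound of 0.187 SD depends on none of these inferences.

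Fourth, the corrected figures assume even recruitment and leave out the four-week transition. Laying out the calendar with the transition, in assumed two-week bins, gives ratios of 2.8 (45 practices) to 3.4 (15 clusters). This makes the discrepancy larger.

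**Conclusion.** The concern holds. The three stated detectable differences come from a closed-cohort calculation and do not apply to a trial with one outcome per patient. With the protocol's ICC of 0.03 and cluster autocorrelation of 0.8, the 45 randomised practices and equal recruitment over six periods, the detectable differences are about 0.281 SD, 0.089 (variance 0.1) and 0.135 (dichotomous). They are about 2.5 times the stated values, or about 2.4 to 3.0 times depending on the cluster unit and on t or normal quantiles. The 80% power claimed at 0.114 SD is about 20%. Power for the hypothesised 0.2 survives on the protocol's own inputs; power for 14 days cannot be judged without an SD in days.

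**What to change.** In section 4.3:

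- Rerun the calculator as a cross-sectional design: complete turnover between periods, no individual autocorrelation, 45 practice clusters in five sequences, six periods and about 3.3 patients per practice-period. Show a small range of ICCs.
- Replace the three stated figures with the results. On the present inputs these are about 0.28 SD, 0.135 (dichotomous) and 0.089 (variance 0.1); they will be somewhat larger if the transition period is modelled.
- Delete the individual-autocorrelation bullet, replace the zero-churn setting with a statement that each patient contributes to one period only, and replace the wording on 60 patients per cluster with 20 per practice.
- Report power for the planned 0.2 beside the detectable differences, and state the SD in days on which the 14-day target relies.

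The cost is protocol wording and one rerun. The published figures become less favourable. The correction itself adds no patients; whether 900 suffices for 14 days depends on the SD assumed.

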6.4 Withdrawal of individual patients

Patients will visit their HCP once for the BiaB study. Afterwards, patient reported outcomes will be collected using questionnaires. Patients can leave the study (stop answering questionnaires) at any time for any reason if they wish to do so without any consequences.

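### The detectable differences in section 4.3 assume the same patients are measured in all six periods; with one outcome per patient they are about 2.5 to 3 times too small.

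*Protocol*

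**What the plan says.** Section 4.3 of the protocol gives the only power statement. The target is set "using a desired power of 80% for the test of the intervention, with a type I (two-tailed) error rate of 0.05", and "The analysis was performed using the US National Institute for Health Stepped-wedge Group-Randomized Trials (SWGRT) Calculator software". Among the inputs, "The intra class correlation was set to 0.03 based on previous data", the cluster autocorrelation is 0.8, the correlation structure is block-exchangeable, and there are 6 periods and 60 patients per cluster. Two further inputs concern the patients themselves: "The expected individual autocorrelation (between two consecutive periods at the level of the patient) was estimated 0.8", and "The churn rate was set to 0.0, as the study consists of one visit for data collection".

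The result for a binary outcome is "sufficient power to detect an absolute difference in effect of 0.055 and a standardized detectable difference of 0.114". For a continuous outcome with variance 0.1 it is "sufficient power to detect an absolute difference in effect of 0.0362 and a standardized detectable difference of 0.1144".

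Elsewhere the design is described differently. Section 6.4 says "Patients will visit their HCP once for the BiaB study". Section 3 has 20 patients per site over the whole 40 weeks, 900 in all. Section 6.1.1 defines one time to diagnosis per patient, taken from the first diagnosis.

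**The concern.** Zero churn combined with an individual autocorrelation means that the same people are measured in every period and act as their own controls when their cluster crosses over. That removes most of the between-patient variance from the treatment comparison. Here nobody is measured under both conditions, and each period brings new patients.

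The reasons given for the two inputs do not support them. A single visit per patient implies complete turnover between periods; the protocol appears to have read churn as dropout. The individual autocorrelation of 0.8 is justified by HCPs following stable guidelines. That is an argument about clusters, and it is the same one given for the cluster autocorrelation.

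The quarterly questionnaires do not make this a cohort for the primary endpoint. They follow a patient who stays in one condition and do not yield a new time to diagnosis in each period.

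If these inputs were really used, the protocol promises a sensitivity that 900 single outcomes cannot give, and a reader could take a null result to exclude benefits that the trial could not have seen.

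**Working it through.** **Model.** Generalised least squares on cluster-period means, with 5 sequences, 6 periods, fixed period effects, an immediate switch and total variance 1. With m patients per cluster-period:

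- variance of a cluster-period mean = ICC + (1 − ICC)/m;
- covariance between periods, closed cohort = ICC × CAC + (1 − ICC) × IAC/m;
- covariance between periods, new patients each time = ICC × CAC.

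CAC and IAC are the cluster and individual autocorrelations. Detectable difference = (t0.975 + t0.80) × SE. Degrees of freedom are clusters − 7 (6 periods plus treatment), a convention the protocol does not state but which matches its figures.

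**Inputs (section 4.3).** ICC 0.03; CAC 0.8; IAC 0.8; 6 periods; 60 patients per cluster; 80% power; two-sided 5%. The 15 clusters (3 per sequence, 15 × 60 = 900) are the reading that fits the printed values.

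**1. The printed figures, as a closed cohort of 60 patients measured six times**

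- SE = 0.03581; df 8, t-sum = 2.306 + 0.889 = 3.195.
- 3.195 × 0.03581 = 0.1144 SD (printed 0.1144).
- 0.1144 × √0.1 = 0.0362 (printed 0.0362).
- 0.1144 × √0.23 = 0.0549 (printed 0.055). Here 0.23 is the mean of 0.3 × 0.7 = 0.21 and 0.5 × 0.5 = 0.25.

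The other readings tried do not give 0.1144: 60 new patients in every cluster-period gives 0.172, a closed cohort of 10 per cluster gives 0.190, and 45 sites of 20 as a closed cohort gives 0.078. The printed calculation therefore used 15 × 60 × 6 = 5,400 outcomes.

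**2. Each patient counted once, ICC and CAC unchanged**

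| | 15 clusters, 60/6 = 10 per period | 45 practices, 20/6 = 3.33 per period |
|---|---|---|
| df | 8 | 38 |
| SE | 0.1065 | 0.0977 |
| Detectable difference (SD) | 0.340 | 0.281 |
| × √0.1 (continuous) | 0.108 | 0.089 |
| × √0.23 (binary) | 0.163 | 0.135 |
| Ratio to 0.1144 | 2.97 | 2.46 |
| Power at 0.1144 SD (noncentral t) | 16% | 21% |

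With ICC from 0.01 to 0.10 and CAC from 0.6 to 1.0, the detectable difference is 0.31–0.40 SD for 15 clusters and 0.27–0.30 SD for 45 practices.

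**3. A check without any stepped-wedge model.** For 900 patients individually randomised 1:1, with no clustering and no period effects, the detectable difference is 2.80 × 2/√900 = 0.187 SD. To detect 0.1144 SD would take (2 × 2.80/0.1144)² ≈ 2,400 patients. The printed claim is out of reach even in that most favourable case.

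**4. The planning effect.** The assumed 0.2 exceeds the corrected absolute figures on both scales (0.089–0.108 continuous, 0.135–0.163 binary). For the target of 14 days out of 70, the largest SD that still gives 80% power is 14/0.340 = 41 days (15 clusters) or 14/0.281 = 50 days (45 practices). The printed 0.1144 would imply 14/0.1144 = 122 days.

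**The case against.** The strongest reply is that the trial was planned on an effect of 0.2, not on 0.0362 or 0.055. With the plan's inputs taken literally, corrected power for 0.2 is over 99% on the continuous scale and about 93% (15 clusters) or 99% (45 practices) on the binary scale. On that view a sensitivity figure is misstated, while the sample size and procedures are unaffected. This stands as a limit on the consequence. It does not rescue the printed figures, and it is itself conditional: variance 0.1, if meant on the relative scale, is an SD of √0.1 × 70 ≈ 22 days. The protocol gives no SD in days.

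Two narrower points also stand.

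- The ratio of 2.97 is the effect of the cohort inputs alone. The ratio of 2.46 also moves from 15 clusters to 45 practices.
- The binary figures depend on a variance convention. Taking the SD at 0.3 plus the difference gives 0.0547 before the correction, and 0.170 or 0.140 after it instead of 0.163 or 0.135. The calculator should supply the final binary value.

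One may add that a null result would be read from its confidence interval. That limits the risk of misreading but does not make the power statement correct.

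**Conclusion.** The concern holds. The churn and individual-autocorrelation inputs contradict the design, and matching 0.1144 and 0.0362 to the printed digits shows that they were used. The detectable differences are understated by a factor of about 2.5 to 3 (2.4 to 2.6 with normal in place of t quantiles), and power at the printed 0.1144 SD is 16–21%.

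The size rests on the protocol's ICC and cluster autocorrelation, equal numbers per period and an immediate switch with no allowance for the transition weeks. It changes little over the ranges tried, and the 0.187 SD floor needs none of the clustering assumptions. What is shown is that the protocol's only power statement is wrong. It is not shown that the trial is underpowered for its assumed 0.2; for the 14-day target that depends on an SD the protocol does not give.

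**What to change.** In section 4.3:

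1. Delete the individual autocorrelation and the zero-churn assumption.
2. State that the design is repeated cross-sectional, with different patients in each period and one outcome per patient.
3. Rerun the calculation with full turnover, the practice as cluster and 20/6 patients per practice-period.
4. Replace 0.055, 0.114, 0.0362 and 0.1144 with the result. For 45 practices expect about 0.135 (binary; 0.140 under the other convention), 0.28, 0.089 and 0.28, before any allowance for the transition.
5. Give the assumed SD of time to diagnosis in days, so that power for 14 days can be read directly.

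The cost is one rerun, a rewritten paragraph and less favourable stated figures. On the plan's own inputs no extra patients are needed; the SD in item 5 will show whether that also holds for the 14-day target.

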6.1 Study parameters/endpoints

For all study endpoints, the analysed population will include patients from usual care and the BiaB intervention period.

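### Section 4.3 calculates detectable differences for a stepped wedge without the 4-week transition that section 3 places at every switch; modelling calendar time, this costs about 11–15% in detectable difference

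*Protocol*

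**What the plan says.** Section 4.3 sets "a desired power of 80% for the test of the intervention" "with a type I (two-tailed) error rate of 0.05" and states "The intra class correlation was set to 0.03 based on previous data". It takes cluster and individual autocorrelations of 0.8, zero churn, a block-exchangeable structure and 60 patients per cluster. For time it states "There are 6 time periods (including usual care and BiaB intervention period" and mentions no transition. It cites advice that the best method is to "simulate the power based on the method of analysis proposed including time in the chosen model". The results are 0.055 absolute and 0.114 standardized for a dichotomous outcome, and 0.0362 absolute with "a standardized detectable difference of 0.1144 (i.e 3.6 and 11.4" per cent for a continuous one.

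Section 3 describes another layout. Usual care lasts a multiple of 6 weeks and is "followed by a transition period of 4 weeks prior to the BiaB intervention" period, itself a multiple of 6 weeks, with 40 weeks per site in total. Twenty patients per site are included for analysis. Section 6.1 says "the analysed population will include patients from usual care and the BiaB intervention period"; it does not mention transition patients.

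**The concern.** Six periods of 6 weeks make 36 weeks; the site runs for 40. The missing 4 weeks fall at a different calendar time in each sequence and sit at the switch, where a stepped wedge gets much of its information. The wedge compares sites on BiaB with sites still in usual care at the same time, and the transition shortens that overlap:

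- Immediate switch: both conditions are present in weeks 6–30, which is 24 of 36 weeks.
- With the transition: sequence 1 starts BiaB at week 10 and sequence 5 leaves usual care at week 30, so both are present in 20 of 40 weeks.
- In weeks 6–10 sequence 1 is in transition and all others are in usual care. In weeks 30–34 sequence 5 is in transition and all others use BiaB.

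At stake is whether the power claimed in section 4.3 belongs to the design in section 3. A rerun that corrected only the treatment of patients as re-measured would still omit the transition.

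**Working it through.** **1. Reproducing the printed figures.** Inputs from section 4.3: 5 sequences × 3 countries = 15 clusters, 60 patients per cluster in each of 6 periods, immediate switch, ICC 0.03, both autocorrelations 0.8, no churn. I used the generalised least squares variance of the treatment effect with categorical period effects and block-exchangeable correlation, and 15 − 7 = 8 degrees of freedom.

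- SE = 0.03581
- Detectable difference = SE × (t₀.₉₇₅,₈ + t₀.₈₀,₈) = 0.03581 × (2.306 + 0.889) = 0.1144
- Continuous: 0.1144 × √0.1 = 0.0362
- Dichotomous: 0.1144 × √0.21 = 0.0524 at p = 0.3. The printed 0.055 needs an averaged variance, (0.21 + 0.25)/2 = 0.23, giving 0.0549; the protocol does not state this.

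The two continuous-outcome figures match every printed digit, so the calculation contained no transition.

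**2. Adding the transition, one outcome per patient.** Assumptions: 45 sites of 20 patients, ICC 0.03, cluster autocorrelation 0.8, sites starting together, recruitment even over the 36 analysed weeks, 4 weeks missing at each switch, normal quantiles (1.960 + 0.842 = 2.802). The same 900 patients are kept in both designs.

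| Design | SE | Detectable difference (SD) | Power at 0.2738 |
|---|---|---|---|
| No transition | 0.0977 | 0.2738 | 80% |
| Transition, 2-week calendar effects | 0.1122 | 0.314 | 68.4% |
| Transition, 6-week calendar effects | 0.1108 | 0.310 | 69.5% |
| Transition, 8-week calendar effects | 0.1094 | 0.306 | 70.6% |
| Transition, 10-week calendar effects | 0.1086 | 0.304 | 71.3% |

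Example, 6-week effects: Φ(0.2738/0.1108 − 1.960) = Φ(0.511) = 69.5%. The SE ratio is 0.1108/0.0977 = 1.134, so 900 patients carry the information of 900/1.134² ≈ 700. With 6-week effects, ICC from 0.001 to 0.2 and cluster autocorrelation 0.8 or 1.0 keep the ratio at 1.11–1.14 and power at 69–71%.

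**3. Adding the transition, closed-cohort inputs of section 4.3 (8 df).** Power at 0.1144 is roughly 65–74% in most calendar-time layouts. It depends on how repeated measures are assigned to calendar cells: single codings reach 77–78%, and layouts that lose a whole cell or add an empty column fall to 54–64%. None reaches 80%.

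**4. Power at the printed 0.1144, one outcome per patient, 45 sites.**

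- No transition: Φ(0.1144/0.0977 − 1.960) = Φ(−0.789) ≈ 21%
- With transition: Φ(0.1144/0.1108 − 1.960) = Φ(−0.928) ≈ 18%, or 17–18% across the calendar codings

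With 15 clusters and 8 df it is about 11–13% with the transition, and the detectable difference is about 0.38 SD.

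**5. Power at the hypothesised 0.2, one outcome per patient, with transition.**

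- Variance 0.1: 0.2/√0.1 = 0.632 SD; power is about 99% or more
- p = 0.3: 0.2/√0.21 = 0.436 SD; power is about 89% (15 clusters, 8 df) to 98% (45 sites)

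**6. Using each site's own period number as time.** The detectable difference then stays at 0.2738. But calendar week = own analysed week + 4 × (BiaB indicator), so a linear calendar trend of b per week adds 4b to the estimated effect.

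**The case against.** Four points deserve weight.

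- A reader might infer that the trial has about 70% power at the printed differences. The documents do not support that. The figure requires each patient to be measured in all six periods, whereas section 4.3 itself says there is one visit. With one outcome per patient, power at 0.1144 is about 21% even without the transition, so the closed-cohort setting is the larger fault.
- A reader might also infer that the sample is too small, or that patients are lost. Neither follows. Section 3 counts 20 analysed patients per site regardless of the transition, and section 4.3 hypothesises 0.2, which remains well powered on its stated variances.
- Section 4.3 asks for time in the model without specifying calendar time, and section 8 leaves technical detail to the SAP. That stands: with own-period coding the detectable difference does not change. That coding, however, carries the 4-week trend bias, so it does not rescue the printed figures. The protocol does not propose it either.
- Section 6.1 does not expressly exclude transition patients, and the figure showing the sequences is not available. Exclusion is the natural reading, not a stated rule.

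What remains is that section 4.3 claims sufficient power for a layout that section 3 does not describe.

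**Conclusion.** The point holds as a relative loss. With calendar time modelled, the transition raises the detectable difference by about 11–15% over the same design without it, and nominal 80% power becomes about 68–71%. This assumes one outcome per patient, a common start, even recruitment and no analysed transition patients. Under the closed-cohort inputs of section 4.3 the size of the loss varies more with layout, but its direction does not. The loss should be corrected together with the closed-cohort setting, because correcting the transition alone would print about 0.13 where the one-visit value is about 0.30–0.31 SD. Whether variances of 0.1 and 0.21 suit a time to diagnosis in days is a separate matter; the adequate power for 0.2 rests on them.

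**What to change.** Rerun section 4.3 on the section 3 layout: 40 calendar weeks, the 4 transition weeks of each sequence set to missing, calendar-time effects and one outcome per patient. Restate the detectable differences, or the power at 0.055, 0.0362 and 0.114, from that run. Expect about 0.30–0.31 SD with 45 sites, that is about 0.31 × √0.1 ≈ 0.10 on the continuous scale. Replace the 6-period assumption with the 40-week layout, and say there that the time effect is calendar time; the model detail can stay in the SAP. Before the rerun, reconcile the shortest BiaB period, which is 3 weeks in the Summary and 6 weeks in section 3 (30 + 4 + 6 = 40).

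The cost is one rerun and a few sentences. The stated figures become less favourable, but no change in sites or patients is needed for the hypothesised 0.2 on the stated variances.
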